1.0 SYNOPSIS

| | |
|---|--|
| Study Title | A Randomized Perspective, Open and Parallel Controlled Study Comparing 3M Tegaderm CHG I.V. Securement Dressing with 3M Tegaderm Transparent Dressing for Evaluation of Antimicrobial Efficacy on DVC Insertion Site in Adult in Critical Care |
| Study Type | post-market |
| Principal Investigator (PI) | Name: [name] Title: [name]: Ruijin Hospital Critical Care Department |
| Device under Investigation Summary | 3M Tegaderm CHG I.V. Securement Dressings This product is composed of a transparent dressing and a gel pad. The gel pad contains 2% (w/w) chlorhexidine gluconate (CHG), which is an antimicrobial agent. This product is suitable for covering and protecting catheter sites (including arterial and venous catheters, intravascular catheters, and percutaneous devices) on the body surface and securing devices to healthy skin. This product should not be used on infected wounds or unhealthy skins. |
| Sponsor | 3M China |
| Purpose | The objective of this study is to evaluate the antimicrobial efficacy of Tegaderm CHG dressing on DVC insertion site in adult patients in critical care |
| Design | This is a single-center, prospective, randomized controlled clinical trial designed to compare the antimicrobial efficacy of Tegaderm CHG I.V. Securement Dressing and transparent dressings for deep vein catheterization in adult ICU patients. Considering the easy-to-distinguish appearances of both products used, this trial will adopt an open-label design. The primary endpoint is the rate of CVC tip colonization (positive catheters after culture/total catheters). Subjects eligible for enrollment will be randomly assigned to either the Tegaderm CHG dressing group or the transparent dressing group, and patients in both groups will be given catheterization according to the hospital's standards and nursed according to the catheter maintenance procedure. The investigator would monitor the subjects during dressing changes, observing the subjects' general conditions, skin condition at the DVC site and the dressing condition, and change a dressing or take relevant measures (if |

| | |
|------------------------------|--|
| | applicable), until the end of the trial, i.e. CVC removal or patient transfer out of the ICU. |

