| | 
 2. There is sunburn, skin infection or scar, mole or other blemishes on the subject's catheterization site that would affect the scoring or measurement of the site; 3. The patient is assessed by the investigator as being at high risk of CLABSI, or known to be CLABSI, based on the environment, duration, and site conditions of catheterization; 4. The patient is documented or known to have allergies (sensitivities) to adhesive products, or other products involved in the trial, e.g. transparent dressings, CHG and alcohol; 5. The patient is being or has been subjected to other antibiotic, catheter or skin-related clinical trials; 6. The patient needs topical application of creams containing antimicrobial ingredients or other antimicrobial fluids beneath the Tegaderm CHG dressing or transparent dressing for skin disinfection, in addition to the requirements of this protocol; 7. The patient is assessed by the investigator as being at high risk of blood stream infection, or known to be sepsis, caused by blood stream infection; 8. The patient has dermatitis, burns, lesions, breaks, eczema, tattoos or other conditions at the catheter insertion site that would interfere with observation in the trial; 9. Women who are pregnant or breast feeding; 10. Patients who are not eligible for the study at the discretion of other investigators. |
| 
Device Regulatory Classification
 | 
The test device is imported Class II medical device with the license of GXZJ No.20163642045. The control device is imported Class II medical device with the license of GXZJ No.20182642129. Both have been registered in China.
 |

| | |
|--------------------------------------|---|
| 
Primary Objective(s)
 | 
The primary objective of this study is compare the difference in the bacterial colonization rate at the CVC tip and the catheterization site on the skin after removal (number of culture-positive cases/total catheters × 100%) between the test and control groups
 |

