5.3 Endpoint(s)

5.3.1 Primary Endpoint(s)

The bacterial colonization rate at the CVC tip and the catheterization site on the skin after removal (number of culture-positive cases/total catheters × 100%)

The primary endpoint is the removal of the CVC from the patient with deep vein catheterization to perform catheter-tip culture and sampling and culture of bacteria from the skin around the insertion site.

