19.1 Statistical Hypotheses

19.2 Sample Size Determination

This study will use a positive two-sided Z test for continuity calibration and use the O'Brien-Fleming expenditure function to determine the test boundary. Assuming a baseline value of 18.7% for CVC tips colonization rate in the control group (this figure is reported by a domestic epidemiological survey) and a reduction rate of 50.0%, each group should contain at least 220 patients with CVC to reach 80% likelihood at 5% significance level. A total of 440 valid cases are required in both groups combined. An interim analysis is scheduled for this study and will be conducted after completion of follow-up visits of 220 subjects to correct for the pre-defined sample size.

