8. INTERIM ANALYSIS

The interim analysis will be performed when enrollment reaches 220 participants, and this interim analysis will be performed by an unblinded team (including statisticians

and programmers) to recalculate the total sample size needed to adjust this study based on the results of the primary endpoint of 220 participants already enrolled and the dropout rate. If the results of the interim analysis show that: When the difference of the primary endpoint between the two dressings, i.e., the positive rate of bacterial culture of the CVC tip segment and skin at the insertion site (either one), is greater than 50% and the p-value is less than 0.005, and with all other considerations to support the objectives and the assumptions of the study were met, the study will be discontinued early with a final statistical analysis report. Otherwise, only issue: The decision to continue as per the protocol or to increase the sample size at a later stage; meanwhile, specific analytical findings were maintained blinded until the entire study was unblinded for final analysis. If the sample size recalculated for the interim analysis was less than or equal to that specified in the protocol, the final analysis was performed when the subsequent test was conducted to the sample size specified in the protocol; if the sample size recalculated for the interim analysis exceeded that specified in the protocol, the final analysis was performed when the subsequent test was conducted to the re-estimated sample size.

In accordance with the O'Brien-Fleming expenditure function, all statistical tests for this interim analysis were two-sided, and p-values less than 0.005 were considered statistically significant for the differences tested.

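### The primary endpoint is the CVC tip alone in some sections and tip plus insertion-site skin in others, and nothing says which outcome decides success or an early stop

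*SAP*

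**What the plan says.** **Tip alone.** The Design row of the Protocol Synopsis states: "The primary endpoint is the rate of CVC tip colonization (positive catheters after culture/total catheters". Protocol 19.2 and SAP 3.2 size the trial on that outcome: "Assuming a baseline value of 18.7% for CVC tips colonization rate in the control group", halved by the test dressing, 220 per group, 80% power, 5% level. Protocol 19.5 recalculates the sample size from the overall tip rate.

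**Tip and skin.** The Synopsis primary objective is to "compare the difference in the bacterial colonization rate at the CVC tip and the catheterization site on the skin after removal". Protocol 5.3.1 gives the primary endpoint as "The bacterial colonization rate at the CVC tip and the catheterization site on the skin after removal". Protocol 5.1 and SAP 2.1, 4.1.1 and 6.3.1 also include skin. Within SAP 6.3.1, the chi-square sentence reads as one item, while the additional mixed model takes tip and skin as separate dependent variables.

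**Interim.** SAP 8 allows an early stop if the difference in "the positive rate of bacterial culture of the CVC tip segment and skin at the insertion site (either one), is greater than 50" per cent, p is below 0.005, and further unspecified considerations support it. It recalculates the sample size "based on the results of the primary endpoint of 220 participants already enrolled and the dropout rate". If "the sample size recalculated for the interim analysis was less than or equal to that specified in the protocol", the planned number stands.

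**Final.** SAP 6.1 applies p < 0.048 to all final tests unless specially described. Protocol 19.4 lists the tip rate among the rates to be tested and omits insertion-site skin, but calls nothing primary.

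**The concern.** Tip and skin can be combined in three ways: either is enough, both are needed, or a positive on one or the other forms a composite. These rules have different error rates, power and required sample sizes. The plan does not choose among them, and its most specific wording, in SAP 8, fits the first and the third.

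Two things are at stake. First, in an open-label trial with an unblinded interim team, the rule for declaring success could be settled after results are known. Second, the 80% power and the 18.7% control rate belong to the tip only. If skin or a composite drives the interim recalculation, the total could stay at 440 when the tip rate would call for more.

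**Working it through.** **Inputs from the documents.** Tip rate 18.7% against 9.35%; 220 per group, 1:1; thresholds p < 0.005 (interim) and p < 0.048 (final), two-sided; interim at 220 of 440, taken as half the information.

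**Assumed, because the documents give no values.** Skin rates, tip–skin correlation and missing-data rates.

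**1. The plan's own figure.** n per group = [z(1−α/2)·√(2p̄(1−p̄)) + z(0.80)·√(p₁(1−p₁) + p₂(1−p₂))]² / (p₁−p₂)², with p₁ = 0.187, p₂ = 0.0935, p̄ = 0.14025. At α = 0.05: (1.960 × 0.4911 + 0.842 × 0.4866)² / 0.0935² = 215.3, so 216. At α = 0.048 it is 219. The stated 220 is thus reproduced from the tip rate alone, without a continuity correction (with one, 237 to 239).

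**2. What the thresholds spend.** The bounds are |Z₁| > 2.807 and |Z₂| > 1.977, with correlation √0.5 between looks. Bivariate normal integration gives a total two-sided error of 4.99% for one outcome. Nothing is left for a second.

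**3. Type I error under each rule** (simulation, neither outcome affected, N fixed at 440, before the >50% condition):

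| Rule | ρ = 0 | 0.3 | 0.5 | 0.7 | 0.9 |
|---|---|---|---|---|---|
| Either at interim, tip only at final | 5.5% | 5.4% | 5.4% | 5.3% | 5.2% |
| Either at both looks | 9.7% | 9.5% | 9.1% | 8.4% | 7.0% |
| Both at both looks | 0.2% | 0.5% | 0.9% | 1.6% | 2.9% |

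Hand check of the second row at ρ = 0: 1 − (1 − 0.0499)² = 9.7%. For the third row, error is at most about 5% when only one outcome lacks an effect.

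**4. The >50% condition.** SAP 8 does not say whether this is relative or absolute. Read as relative, in either direction, with 110 per group and an assumed 30% skin rate in both arms, it cuts the chance of a null skin crossing at p < 0.005 from 0.51% to 0.13%, a reduction of (0.51 − 0.13)/0.51, about three quarters. At an assumed 18.7% skin rate it removes almost none.

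**5. Composite.** One test, so no inflation. The control rate would be p_t + p_s − [p_t·p_s + ρ√(p_t(1−p_t)p_s(1−p_s))]. With an assumed skin rate of 18.7%, this is 33.9% at ρ = 0 and 23.3% at ρ = 0.7, not 18.7%.

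**6. Power if both must win** (220 per group, no continuity correction, ρ from 0 to 0.7). Tip alone: 81%. Both:
- skin 18.7% to 9.35%: 66% to 73%
- skin 30% to 15%: 78% to 80%
- skin 30% to 21%: 47% to 55%

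**7. Recalculated sample size.** SAP 8 gives no formula, so assume a fixed 50% reduction and apply step 1 at α = 0.05. A 15% tip rate needs 278 per group (556 in total). A 30% skin or composite rate needs 121 per group (242), which leaves the total at 440. At 220 per group, power for a 15% tip rate is about 70%.

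**The case against.** The strongest reply is that the interim clause does little harm on its own. SAP 8 attaches three further conditions to a stop, and step 3 shows that, with the tip alone deciding at the end, the clause adds at most about 0.5 points, often less once the >50% condition applies. That stands.

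A reader might infer that SAP 8 lets a skin result by itself stop the trial. The text does not go so far: the parenthesis may define a composite, and under either reading the other conditions also apply.

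A reader might also infer from Protocol 19.4 that the tip is the defined primary. That section only lists tested rates, so omitting skin there is a gap and not a definition. Likewise, "19.1 Statistical Hypotheses" appears as a heading with no text beneath it. This may be lost text and carries no weight, although the SAP supplies no hypothesis or decision rule either.

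The recalculation split is not an independent fault. SAP 8 refers to the primary endpoint, which conflicts with Protocol 19.5 only if skin is part of it.

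Finally, making skin secondary is a design choice, since the formal objective and endpoint sections include it. That is fair. The requirement is one stated rule with matching power, and tip-only is simply the rule that fits the stated sample-size basis.

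None of this removes the contradiction over what the primary endpoint is.

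**Conclusion.** The contradiction is in the current text, and the success criterion is undefined. It must be settled before the interim analysis.

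Its size depends on the rule. Error is 5.0% if one named outcome decides, and at most about 5.5% if either can stop the trial but only the tip counts at the end. It is tempting to report 9.7% as the trial's error rate. The documents do not support that: the range 9.7% to 7.0% needs a rule that either outcome also wins at the final analysis, which is neither stated nor excluded. A composite does not inflate error but makes the 18.7% rate inapplicable. A both-must-win rule controls error, but the 80% power was not planned for it.

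These figures rest on a fixed total of 440, an interim at half the information, and an assumed correlation of 0 to 0.9.

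A reader might also conclude that tip colonization with missing outcomes filled as positive is fully supported by the 80% figure. It is not, because that power assumes no filled outcomes. At 220 per group, filling m of each arm changes a rate p to m + (1 − m)p, and power falls from 81% to about 67%, 56% and 39% at assumed missing rates of 5%, 10% and 20%.

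**What to change.** Before any interim data are seen:

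1. State one deciding rule and use it in the Synopsis, Protocol 5.1, 5.3.1, 19.1, 19.2 and 19.5, and SAP 2.1, 4.1.1, 6.3.1 and 8.
2. The rule that matches the stated sample-size basis is CVC-tip colonization as the sole primary, efficacy-stopping and recalculation outcome. Delete the either-one parenthesis in SAP 8. Test insertion-site skin as first secondary, only if the tip is significant, at the level of the look where the tip wins (0.005 or 0.048).
3. Name one deciding unit (participant or catheter), one test and one analysis set. SAP 6.3.1 lists both units, chi-square or Fisher plus a mixed model, and both FAS and PPS; SAP 5.1 already ranks FAS first.
4. Reconcile the worst-case filling in Protocol 19.3 and SAP 5.1 and 7.3 with Protocol 19.6, which says efficacy data will not be imputed. Then restate power with missing outcomes allowed for.
5. If skin stays primary, state a both-must-win rule, an alpha split or a defined composite, and restate the power. An equal split would need thresholds of about 0.0015 and 0.0244 per outcome and about 263 per group for the tip, without continuity correction.

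The cost is a protocol amendment and SAP revision. Option 2 in itself needs no extra subjects or data, but a skin-only effect could no longer carry the trial. The unblinded increase in sample size allowed by SAP 8 is a separate matter that this change does not resolve.

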9. DESCRIPTION ABOUT THE PLAN

<This Statistical Analysis Plan (SAP) provides a more technical and detailed description of the efficacy and security index than the study protocol (version v1.0, dated 2020.8.25>) and proposes specific statistical analysis methods for the relevant evaluation indicators, taking into account the numerical characteristics of the indicators in the study protocol and the specific requirements of this study. The tables, graphs, and lists associated with this plan will be provided in a separate, unique file.
